7.3 Multiple Comparisons

Each co-primary endpoint will be tested for superiority to placebo at a two-sided alpha level of 0.05 without further adjustment for multiplicity. If the primary endpoint tests are both

significant, then the key secondary endpoints are evaluated using the procedure, conducted at alpha=0.05.

The Hochberg Procedure works as follows:

Step 1: Conduct all of your statistical tests and find the p-value for each test.

Step 2: Arrange the p-values in order from smallest to largest, assigning a rank to each one – the smallest p-value has a rank of 1, the next smallest has a rank of 2, etc.

Step 3: Calculate the Hochberg critical value for each p-value, using the formula $(i/m)*Q$, where:

i = rank of p-value

m = total number of tests

Q = your chosen false discovery rate

Suppose a 10% false discovery rate, with 5 tests, to calculate the Hochberg critical value for each p-value, we can use the following formula: $(i/5)*0.1$ where i = rank of p-value.

Step 4: Find the largest p-value that is less than the critical value. Designate every p-value that is smaller than this p-value to be significant.

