9.4.2 Secondary Endpoint(s)

If the primary endpoint tests are both significant, then the key secondary endpoints are evaluated using the Hochberg procedure, conducted at alpha=0.05.

Like the co-primary endpoints, all of the key secondary endpoints are all binary endpoints. Hence the key secondary endpoints will be analyzed in the same manner as the primary endpoint. In particular they will be analyzed using Cochran-Mantel methodology to estimate the common risk difference, and are stratified by the use of prophylactic migraine medication (yes or no) and country (China or Korea).

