9.4.3 Control of multiplicity

As discussed above, the co-primary endpoints are both tested at alpha=0.05. No correction for multiplicity is needed, since both co-primary endpoints must be positive for the study to be positive. The secondary endpoints are protected by a gate-keeper procedure. If both of the co-primary endpoints are significant, only then will the key secondary endpoints be tested for significance. Within the family of key secondary endpoints, multiplicity is controlled using the Hochberg procedure.

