7.6.2 Key Secondary Efficacy Analyses

If the co-primary endpoint tests are both significant, then the key secondary endpoints are evaluated using the Hochberg Procedure. See [Section 7.3](#) for details on the procedure.

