7.6.2.5 Sustained Pain Freedom from 2 to 48 Hours

Sustained pain freedom is assessed using the number of mITT subjects that experienced no headache pain (response of 0 on Likert scale) at all time points from 2 through 48 hours post-dose. Subjects with missing pain scores at no more than 1 time point, given that they have responses of no pain (response of 0 on Likert scale) at the 2, 24, and 48 hour time points will be considered as successes. Subjects with responses missing at greater than 1 time point; missing data at the 2, 24, or 48 hour time point (NC1=F); or with any pain score greater than 0; or with any rescue medication within 48 hours (RM=F) will be considered as failures.

The proportion of mITT subjects who have a response of sustained pain freedom from 2 to 48 hours will be evaluated using the same methodology described in section [7.6.1.1](#).

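### SAP 7.3 names the Hochberg procedure for the five key secondary endpoints but writes out Benjamini-Hochberg steps, with Q unset and a faulty last step, so the written rule is not the protocol's rule

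*SAP*

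**What the plan says.** Protocol 9.4.2 states that, once both co-primary tests succeed, "the key secondary endpoints are evaluated using the Hochberg procedure, conducted at alpha=0.05". Protocol 9.4.3 gives the purpose: "Within the family of key secondary endpoints, multiplicity is controlled using the Hochberg procedure". SAP 7.6.2 repeats the name and points elsewhere for the mechanics: "evaluated using the Hochberg Procedure. See [Section 7.3](#) for details on the procedure".

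SAP 7.3 is therefore the operative algorithm. Its lead sentence carries alpha=0.05 and its steps are headed as the Hochberg procedure. The steps then say:

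- Step 3: "Calculate the Hochberg critical value for each p-value, using the formula $(i/m)*Q", with ranks running from the smallest p-value upwards and "Q = your chosen false discovery rate".
- The only number attached to Q is an illustration: "Suppose a 10% false discovery rate, with 5 tests".
- Step 4, after finding the largest p-value below its cut-off: "Designate every p-value that is smaller than this p-value to be significant".

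SAP 7.10 declares no change from the protocol's planned analyses.

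**The concern.** The steps depart from the Hochberg procedure in three ways.

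1. The cut-offs are those of Benjamini-Hochberg, which targets the false discovery rate. Hochberg's procedure targets the chance of any false claim in the family.
2. Q is never tied to the stated alpha.
3. Step 4 rejects only p-values strictly below the largest passing one, so the passing p-value itself is always lost.

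The first and third errors pull in opposite directions: the cut-offs are too lenient at ranks 2 to 4, and the printed last step is too strict.

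All five key secondary claims depend on this rule. One competent programmer following the name and another following the steps could report different claims from the same data. Choosing between them after unblinding would be a post hoc decision.

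**Working it through.** **Inputs.** m = 5 key secondary endpoints (SAP 4.2.1). Alpha = 0.05 (Protocol 9.4.2; SAP 7.3 lead sentence), two-sided (SAP 7.6.1.1, whose method the key secondaries use).

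**Cut-offs.** Hochberg uses alpha/(m−i+1); the SAP uses (i/m)×Q.

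| Rank i | Hochberg, 0.05/(6−i) | SAP, Q=0.05 | SAP, Q=0.10 | Q needed to match Hochberg |
|---|---|---|---|---|
| 1 | 0.0100 | 0.01 | 0.02 | 0.05 |
| 2 | 0.0125 | 0.02 | 0.04 | 0.03125 |
| 3 | 0.0167 | 0.03 | 0.06 | 0.0278 |
| 4 | 0.0250 | 0.04 | 0.08 | 0.03125 |
| 5 | 0.0500 | 0.05 | 0.10 | 0.05 |

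The last column is (5/i)×0.05/(6−i). It is not constant, so no single Q reproduces Hochberg. Step 4 as printed cannot reproduce it either, because it can never reject all five.

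**Hand examples (number of claims, Q=0.05).** Inclusive means that the largest passing p-value is also rejected.

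| Ordered p-values | Hochberg | SAP cut-offs, inclusive | SAP as printed |
|---|---|---|---|
| 0.005, 0.018, 0.028, 0.038, 0.20 | 1 | 4 | 3 |
| 0.001, 0.002, 0.003, 0.004, 0.045 | 5 | 5 | 4 |
| 0.004, 0.2, 0.3, 0.4, 0.5 | 1 | 1 | 0 |

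In the first row, 0.038 passes 0.04, so the inclusive rule takes ranks 1 to 4 and the printed rule ranks 1 to 3. Under Hochberg, 0.038 > 0.025, 0.028 > 0.0167 and 0.018 > 0.0125, so only 0.005 ≤ 0.01 survives.

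**Closed form.** Take two independent true nulls and three endpoints with p near zero, so the nulls hold ranks 4 and 5.

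- SAP cut-offs, inclusive, Q=0.05: 1 − 0.96² + 0.01² = 0.0785.
- Hochberg: 1 − 0.975² + 0.025² = 0.0500.
- SAP as printed, Q=0.05: a true null is rejected only if both nulls are at or below 0.05, so 0.05² = 0.0025.

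**Simulation.** Five two-sided z-tests, exchangeable correlation 0, 0.5, 0.7 or 0.8, one to five true nulls, the other endpoints shifted by 8, 3 or 2 standard errors (SE): 60 scenarios, 400,000 replicates each. Family-wise error (%) for the SAP cut-offs with an inclusive last step, Q=0.05, at 2/3/4 true nulls:

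| Correlation | 8 SE | 3 SE | 2 SE |
|---|---|---|---|
| 0 | 7.9/8.8/7.9 | 6.8/7.6/6.8 | 4.5/5.3/5.5 |
| 0.5 | 7.4/7.8/6.8 | 5.6/6.2/5.7 | 4.4/5.1/5.1 |
| 0.7 | 6.7/6.9/5.9 | 4.7/5.1/4.8 | 4.3/4.7/4.6 |
| 0.8 | 6.3/6.2/5.3 | 4.2/4.4/4.2 | at most 4.4 |

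With one or five true nulls the error is about 5.0% or less. True Hochberg stays at or below about 5.0% throughout. The steps as printed at Q=0.05 never exceed 3.1%.

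**Power.**

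- One 8 SE effect among four independent nulls: the printed rule declares it in 7.8% of trials, because it needs a null to pass as well. The inclusive rule declares it in 100%.
- Five true effects of 3 SE at correlation 0.5: mean claims are 3.91 (Hochberg), 4.08 (inclusive) and 3.14 (printed). The number of claims differs from Hochberg in 10.9% of trials for the inclusive rule and 88% for the printed rule.

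**Plausibility of the effect sizes.** Protocol 1.3.2 gives Phase 2b rates for two of the five endpoints. At 600 per arm with unpooled SE:

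- Pain relief at 2 hours, 72.1% against 51.2%: 0.209/0.0274 = 7.6 SE.
- Sustained pain freedom 2 to 24 hours, 27.9% against 7.4%: 0.205/0.0212 = 9.7 SE.

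Strong effects on some endpoints are therefore realistic. The documents give no correlations. Independence is an upper case: success on the 48-hour endpoint requires that the subject "experienced no headache pain (response of 0 on Likert scale) at all time points from 2 through 48 hours post-dose", which nests it in the 24-hour endpoint.

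**The case against.** - **The intent is clear.** Both documents name Hochberg and both give alpha=0.05, so an analyst following the name would do the right thing. That stands as evidence of intent and makes the correction uncontroversial. It does not settle what is run, because SAP 7.6.2 sends the programmer to SAP 7.3 and no other section gives correct steps.
- **Q=0.05 is the natural reading, and the 10% is only an example.** Agreed. At Q=0.10 the inclusive rule would give 15.3/17.1/15.3% (independent, 8 SE, 2/3/4 nulls) and the printed rule up to 6.5%, but the SAP does not select that value and the conclusion does not rest on it. At Q=0.05 ranks 2 to 4 are still too lenient.
- **The inflation belongs to a rule the SAP does not print.** This is correct: it arises only if the analyst repairs Step 4 and keeps Step 3. The repair is likely, since it yields the standard Benjamini-Hochberg procedure. Read literally at Q=0.05, the rule is conservative and the loss is power.
- **The largest figures need independence, strong effects and several true nulls together.** This also stands. With correlation 0.8 and effects of 3 SE or less there is no excess over 5%, and earlier trials reported benefit across many secondary endpoints (Protocol 1.3), so two to four true nulls may be unlikely. The contradiction between the rules needs none of these assumptions.

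**Conclusion.** The concern holds: SAP 7.3 is wrong as written, not merely short of detail, and must be fixed. That the steps differ from Hochberg follows from the formulas alone.

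The consequence depends on how an analyst resolves the text. With Step 4 repaired and Q=0.05, family-wise error can reach 8.8%, or 5.3% to 6.3% at correlation 0.8 with strong effects and two to four true nulls. With Step 4 as printed and Q=0.05, error is at most 3.1%, and genuine effects are missed. The sizes rest on assumed effect sizes, correlations and numbers of true nulls.

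Neither document uses the term family-wise. That target is inferred from the named procedure, its alpha and the stated purpose of controlling multiplicity. The co-primary tests and the gate to the key secondaries are not affected.

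**What to change.** Before unblinding, replace Steps 3 and 4 of SAP 7.3 with: order the five p-values p(1) ≤ … ≤ p(5); find the largest i with p(i) ≤ 0.05/(5−i+1); reject the hypotheses ranked 1 to i inclusive; if no i qualifies, reject none. State two-sided alpha=0.05 and m=5, and list the cut-offs 0.0100, 0.0125, 0.0167, 0.0250 and 0.0500. Delete Q, the false-discovery-rate wording and the 10% example.

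The cost is a few lines of SAP text and one line of code, with no change to data collection or sample size. In the case of five 3 SE effects at correlation 0.5, mean claims fall from 4.08 to 3.91 against the inclusive reading and rise from 3.14 to 3.91 against the printed one.

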7.4 Data Handling Conventions

7.4.1 Premature Withdrawal and Missing Data

For efficacy analyses, partial or missing dates will not be imputed. The relative study days, where determined, will be calculated for full dates only.

For rescue medication, if the time of rescue medication is missing, then all endpoints on or after the date of rescue medication will be imputed as failures.

For missing start date of AE or prior/concomitant medication, the following rules will be applied:

- If the start date is completely missing, the start date will be equal to the first dose date of study drug. However, if the stop date is not missing and is before the first dose date of study drug, then the stop date will be used instead.
- If the start day and month are missing and year is present, then the first day of the first month (January) will be used. However, if the year is the same as the year of first dose date, then the start date will be equal to the first dose date.
- If the start day is missing and year and month are present, the first day of that month will be used. However, if the year and month are the same as the year and month of first dose date, then the start date will be equal to the first dose date.

For missing stop date of AE or prior/concomitant medication, the following rules will be applied:

- If the stop date is completely missing and the medication is not ongoing, the stop date will be equal to the date of completion/withdrawal, whichever is the latest. Otherwise, if the stop date is completely missing, it will not be imputed.
- If the stop day and month are missing and year is present, then the last day of the last month (December) will be used. However, if the year is the same as the year of date of completion/withdrawal, then the stop date will be equal to the date of completion/withdrawal.
- If the stop day is missing and year and month are present, the last day of that month will be used. However, if the year and month are the same as the year and month of date of completion/withdrawal, then the stop date will be equal to the date of completion/withdrawal.

These imputed dates will be used to determine whether the AEs or medications are on-treatment.

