5.4.1 Rescue Medications

After dosing with study medication, all other headache medication is prohibited during the 2 hours post dose. However, a subject who does not experience relief of their migraine headache at the end of two hours after dosing with study medication (and after the two hour assessments have been completed on the eDiary), will be permitted to use the following rescue medication: aspirin, ibuprofen, acetaminophen up to 1000mg/day (this includes Excedrin Migraine) naprosyn (or any other type of non- steroidal anti-inflammatory (NSAID)), antiemetics (e.g., metoclopramide or promethazine), or baclofen. These are the only medications allowed for rescue treatment after 2 hours post dose of study medication.

However, if needed, after 48-hours of administering the one dose of study medication (and before coming in for the End of Treatment Visit) subject may take their prescribed standard of care medications for treatment of migraine (including triptans if not contraindicated, provided all of the assessments have been completed on the eDiary. Similarly, if the migraine is relieved by study medication at 2 hours after dosing but then recurs to a moderate or severe intensity level between two and forty-eight hours, the subject will be permitted to take the same rescue therapy as outlined above. In all circumstances, the subject will always continue to complete his or her eDiary entries through the 48-hour assessment after consuming the study medication. Use of concomitant medication after randomization, including rescue medication, will be recorded by the subject on a paper diary (Concomitant, Adverse Event and Rescue Medication Log) and reported to the site. The site will record medications that were taken within 14 days of dosing with study medication (or until the End of Treatment Visit).

During the 45 days the subject is participating in the study, if the subject has a nonqualifying migraine (mild migraine) or a migraine that they do not treat with study medication, the subject is permitted to use only the following medications: aspirin, ibuprofen, naprosyn (or any other type of non- steroidal anti-inflammatory (NSAID)), antiemetics (e.g., metoclopramide or promethazine), or baclofen.

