6.3.3 Rescue Medication

The subject's use of rescue medication is recorded by the subject in a paper diary.

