9 STATISTICS

9.1 General Procedures

Categorical variables are tabulated with counts and percentages. Continuous variables are summarized with univariate statistics (e.g., n, mean, standard error, median, minimum and maximum).

For the calculation of descriptive statistics of observed data, subjects must have an initial value (e.g. baseline value) to be evaluable for endpoints based on values and changes from the initial value over time.

Tabulations of the following endpoints present the number of unique subjects with an event: protocol deviations; interruptions of study therapy; non-study medications; adverse events; and laboratory abnormalities. Thus, for these endpoints, multiple occurrences of the same event are counted only once per subject.

For the assessments of most endpoints, if a subject uses rescue medication before the endpoint data have been fully collected then the subject will be considered a failure on that endpoint. Full details will be provided in the statistical analysis plan.

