9.4 Statistical Methods

9.4.1 Primary Endpoint(s)

BHV-3000 (rimegepant) is tested for superiority to placebo, at an alpha=0.05 level, on both the co-primary endpoints of pain freedom at 2 hours post-dose and freedom the most bothersome symptom at 2 hours post-dose.

Both endpoints are evaluated using Cochran-Mantel Haenszel methodology to estimate the common risk difference, and are stratified by the use of prophylactic migraine medication (yes or no) and country (China or Korea). These tests are conducted using the mITT subjects, with missing data at two hours imputed to be failure (i.e., Non-Completers = Failure; NC=F). Subjects that use rescue medication prior to reporting their co-primary endpoints will be classified as failures. Sensitivity analyses are described in the Statistical Analysis Plan (SAP).

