9.4.4 Missing Data

As discussed above, missing data for the co-primary endpoints is handled using a composite variable strategy, with missing data imputed to be failure (NC=F). In addition, subjects taking rescue medications prior to reporting their co-primary endpoints will be classified as failure.

The first two key secondary endpoints, pain relief at 2 hours post-dose and the ability to function normally at 2 hours post-dose, are binary endpoints and identical in structure to the co-primary endpoints. Hence, these two key secondary endpoints will be handled with the same composite variable strategy as is applied to the coprimary endpoints.

The third key secondary endpoint, use of rescue medications through 24 hours post-dose will be handled in a similar manner, with NC=F. However, since the use of rescue medications is the endpoint of interest, this is not treated as an intercurrent event.

The fourth and fifth key secondary endpoints, sustained pain freedom from 2 to 24 hours post dose, and from 2 to 48 hours post-dose, are with handled with a similar composite variable strategy. Subjects that use rescue medications before reporting the last data for an endpoint, either at 24 or 48 hours, will be classified as failures. Since subjects will need to sleep over periods as long as 24 or 48 hours, the requirement that non-completers be classified as failures is relaxed slightly. For these variables, subjects with more than 1 missing data point, other than at the critical 2, 24 or 48 hour data points, are classified as failures. For example, for sustained pain freedom from 2 to 24 hours, the subjects are expected to provide data at 2, 3, 4, 6, 8, and 24 hours. The data at 2 and 24 hour time points must be present or the subject is classified as a failure. However, any single data point may be missing at 3, 4, 6 or 8 hours without penalty. For sustained pain freedom from 2 to 48 hours, the data at 2, 24, and 48 hours are required to be present.

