7.6.1.1 Pain Freedom at 2 Hours Post-Dose

Pain freedom is assessed using the number of mITT subjects that report pain levels of “none” at 2 hours post-dose on a 4-point Likert scale (0=none, 1=mild, 2=moderate, 3=severe). The information from the 4-point scale is directly summarized as follows:

A table showing descriptive statistics for the observed data, which includes the number and percentage of subjects reporting each of the 4 pain levels at baseline and each post-dose timepoint, and the percentage of subjects with missing data, for each treatment group. The table will include exact (Clopper-Pearson) 95% CIs for each percentage.

The difference in percentage of pain freedom at 2 hours post dose between treatment groups is evaluated by computing the common risk difference, using Cochran-Mantel-Haenszel (CMH) weights (sample size weights), stratified by the use of prophylactic migraine medication (yes or no) and country (China or Korea). The risk difference is tested at a two-sided alpha level of 0.05. Missing data at 2 hours post-dose will be imputed as failures (i.e., non-Completers = Failure; NC=F). Subjects that use rescue medication prior to reporting pain freedom at 2 hours will be classified as failures (i.e., Rescue Medication = Failure; RM=F). If a stratum (prophylactic medication use: yes or no) has sparse data (less than 5 subjects), then the strata will be pooled.

A forest plot of the risk differences within each stratum, and common risk difference (similar to the risk difference plot produced by SAS Proc Freq) will be provided.

Sensitivity analyses will be conducted as follows:

1. The primary analysis is repeated, using the mITT population, with missing data at 2 hours post-dose imputed using Last Observation Carried Forward (LOCF). Baseline Observation Carried Forward (BOCF) is permitted.
2. The primary analysis is repeated using only data from complete cases (data present at baseline and 2 hours).

A sample SAS code for exact (Clopper-Pearson) 95% CIs is the following:

```
proc freq data=pain;
  by treatment pain_level;
  table response / binomial (level="1" CL=(EXACT));
  weight count;
run;
```

A sample SAS code for common risk difference from Mantel Haenszel method is the following:

```
proc freq data=pain_2h;
  table prophylactic_migraine_medication*country*treatment*response /riskdiff (common
  CL=(WALD)) CMH ;
  weight count;
run;
```

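### A same-day rescue entry with no clock time turns a recorded 2-hour success into a failure on both co-primary endpoints, and no sensitivity analysis varies that rule

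*SAP*

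**What the plan says.** SAP 7.4.1 has one sentence for rescue records that lack a clock time: "if the time of rescue medication is missing, then all endpoints on or after the date of rescue medication will be imputed as failures". It goes by calendar date and makes no exception for a value already captured in the eDiary.

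Elsewhere the plan goes by the order of events:

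- Protocol 9.4.1: "Subjects that use rescue medication prior to reporting their co-primary endpoints will be classified as failures". Protocol 9.4.4 repeats the condition: "subjects taking rescue medications prior to reporting their co-primary endpoints will be classified as failure".
- SAP 7.6.1.1, for pain freedom: "Subjects that use rescue medication prior to reporting pain freedom at 2 hours will be classified as failures". SAP 7.6.1.2 sets the same condition for MBS freedom.
- Protocol 5.4.1 bars other headache medication for 2 hours after dosing and opens rescue only after that point ("and after the two hour assessments have been completed on the eDiary"). It also allows rescue for a recurrence up to 48 hours.
- SAP 7.6.3.3 counts a subject who is pain-free at 2 hours, records rescue and has no pain severity recorded as a relapse. It therefore places that rescue after the 2-hour report.

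On data sources, Protocol 6.3.3 says that a subject's "use of rescue medication is recorded by the subject in a paper diary", while pain and symptoms go into the eDiary. The two sensitivity analyses for each co-primary endpoint (SAP 7.6.1.1 and 7.6.1.2) are LOCF for missing 2-hour data and complete cases.

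**The concern.** Take a hypothetical subject who doses at 09:00, is pain-free and MBS-free in the eDiary at 11:00, has a recurrence at 20:00, and logs ibuprofen with a date but no time. The endpoint sections would count this subject as a success on both co-primaries, because the rescue followed the report. Read literally, SAP 7.4.1 makes the subject a failure on both. It does the same to the 2-hour key secondary endpoints (pain relief, normal function) and to the 15 to 90 minute endpoints.

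Observed co-primary data would then be replaced because of a blank field in a separate paper record, and partly because of what happened after 2 hours. For a subject who followed the rescue rules, the imputed order is the opposite of the true one. MBS freedom is the more exposed endpoint. A subject can be MBS-free at 2 hours, still be in pain, and take permitted rescue straight after reporting. A pain-free subject reaches permitted rescue only through recurrence to moderate or severe pain.

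**Working it through.** **1. The plan's own power figures.** Inputs from Protocol Appendix IV: 600 per arm, Pearson chi-square, two-sided alpha 0.05, pain freedom 14% versus 22%, MBS freedom 28% versus 38%. Power = Φ((d - 1.96·SE0)/SE1), with SE0 from the pooled rate and SE1 from the separate rates.

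- Pain: SE0 = √(2 × 0.18 × 0.82/600) = 0.0222; SE1 = √((0.14 × 0.86 + 0.22 × 0.78)/600) = 0.0221; power 95.1% (stated 95.1%).
- MBS: SE0 = √(2 × 0.33 × 0.67/600) = 0.0271; SE1 = √((0.28 × 0.72 + 0.38 × 0.62)/600) = 0.0270; power 95.85% (stated 95.8%).
- Joint power under independence: 0.9511 × 0.9585 = 91.2%. The plan's rounded version is 0.95 × 0.95 = 0.9025.

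The stated figures reproduce.

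**2. How many MBS successes could be overwritten.** The documents give neither the rescue rate among 2-hour responders nor the share of entries without a time, so both are assumptions. MBS rates of 36% and 27% are chosen near the Appendix IV results. Missing-time share m = 5% to 20%.

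Overwritten share per arm = MBS rate × later same-date rescue rate × m. Shift in the difference = placebo loss - rimegepant loss.

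| Assumed rescue (rimegepant / placebo) | Rimegepant loss | Placebo loss | Shift |
|---|---|---|---|
| 15% / 30% | 0.36 × 0.15 × m = 0.27% to 1.08% (1.6 to 6.5 of 600) | 0.27 × 0.30 × m = 0.41% to 1.62% (2.4 to 9.7 of 600) | +0.14 to +0.54 points |
| 20% / 20% | 0.36 × 0.20 × m = 0.36% to 1.44% | 0.27 × 0.20 × m = 0.27% to 1.08% | -0.09 to -0.36 points |

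The sign turns on one ratio: the shift is positive only if the placebo rescue rate among MBS-free subjects exceeds the rimegepant rate by more than 0.36/0.27 = 1.33 times.

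Scale: the standard error of the MBS difference is √(0.36 × 0.64/600 + 0.27 × 0.73/600) = 2.7 points, so the largest shift is 0.54/2.7 = 0.2 standard errors. The MBS gains in the three earlier studies were 8.3 to 12.4 points.

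**3. Effect on power if both arms lose the same share f of responders.** Each rate in step 1 is multiplied by (1 - f).

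| f (assumed) | Pain difference | MBS difference | Joint power |
|---|---|---|---|
| 0 | 8.0 | 10.0 | 91.2% |
| 1% | 7.9 | 9.9 | 90.7% |
| 2% | 7.8 | 9.8 | 90.2% |
| 5% | 7.6 | 9.5 | 88.7% |

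The equal-rescue case in step 2 corresponds to f = 0.20 × (0.05 to 0.20) = 1% to 4%.

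**4. Which dates matter.** The rule reaches the 2-hour endpoint when the rescue date is on or before the date of the 2-hour report. For a dose at 23:00 the report falls on the next day. An untimed rescue dated the dosing day then did precede the report, and failure is right. An untimed rescue dated the next day may have come before or after it. The useful comparison is therefore with the date of the 2-hour report, not the date of dosing.

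**The case against.** The strongest defence is that the sections address different situations. The endpoint sections cover rescue known to precede the report, and SAP 7.4.1 covers an unknown order. Protocol 9.1 sets the general principle ("if a subject uses rescue medication before the endpoint data have been fully collected then the subject will be considered a failure on that endpoint") and leaves full details to the SAP. The rule is prespecified, is the same in both arms, and agrees in spirit with counting non-completers as failures. This stands: the rule is a legitimate worst case, not a breach of the protocol. It does not explain why observed data should be replaced with no look at the alternative, or how the rule fits with SAP 7.6.3.3.

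Four stronger readings are tempting, and the documents do not support them.

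- *That missing times will be common.* A paper diary makes them possible, but no rate is given. SAP 7.6.2.3 lists date and time of rescue as data items, and the diary is returned at a visit within 7 (+2) days, when gaps can be queried.
- *That the bias favours rimegepant.* That needs the assumed 15% versus 30% split. Rescue use as a key secondary endpoint concerns all mITT subjects and says nothing about 2-hour responders. With equal rescue use the shift goes the other way.
- *That a real relapse disappears.* In the example, the recurrence falls between the 8-hour and 24-hour diary entries, so the no-severity rule of SAP 7.6.3.3 may count it. The documents do not say which section governs.
- *That a missing date is treated more leniently than a missing time.* SAP 7.4.1 says "For efficacy analyses, partial or missing dates will not be imputed", but it also sets a completely missing medication start date, in general, to the first dose date in order to decide on-treatment status. How an undated rescue record counts for efficacy is unclear, and no more than that.

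**Conclusion.** The point holds as a gap in prespecification. One sentence in SAP 7.4.1 can replace recorded 2-hour successes on both co-primary endpoints with failures in subjects whom the endpoint sections would not fail. Both planned sensitivity analyses leave that sentence in force, because they change only how missing 2-hour data are handled. SAP 7.4.1 and 7.6.3.3 also give different answers for a subject who is pain-free at 2 hours and has an untimed rescue that day.

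The size is probably small. On assumed rates (5% to 20% of entries without a time; later same-date rescue of 15% versus 30%, or 20% in both arms), the MBS difference moves by about -0.4 to +0.5 points. Equal loss of 1% to 5% of responders would lower joint power from 91.2% to between 90.7% and 88.7%. The direction cannot be known from the documents. This is unlikely to decide the trial, but it concerns the co-primary results and is easy to settle before unblinding.

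**What to change.** In SAP 7.4.1, compare the date of an untimed rescue entry with the actual date of the 2-hour eDiary report:

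1. If the rescue date is on or after dosing and earlier than the date of the report, rescue came first. Apply RM=F.
2. If the two dates are the same, the order is unknown. Prespecify both (a) keeping scores recorded at or before the 2-hour report and applying RM=F to all later time points, and (b) the present all-fail rule. Name one as primary and run the other as a sensitivity analysis of both co-primary endpoints.
3. Report the number of affected subjects by arm.
4. Reconcile SAP 7.4.1 with 7.6.1 and 7.6.3.3, and state which section governs a 2-hour pain-free subject with untimed same-day rescue.

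The cost is SAP wording and one extra run per co-primary endpoint. No data collection changes. Option (a) assumes that subjects followed the rescue timing rules, and option (b) assumes that they did not, which is why both should be shown.
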